10.3.2.6. Adverse Events by Maximum Severity Grade Level

Treatment-emergent adverse events will be summarized by maximum CTCAE grade level of each preferred term. Each preferred term will be assigned to a grade level based on severity and seriousness, adapted from CTCAE Version 4.03 for grading severity of adverse events.

All serious adverse events will be categorized according to Grade definition.

If a patient has a non-serious adverse event with unknown grade, then the patient will be counted in the severity grade level category of "unknown," even if the patient has another occurrence of the same event with a grade present.

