1.2. Glossary of Definitions

Abbreviations list pertains to the SAP only.

Abbreviation	Description
AE	Adverse Event: Any untoward medical occurrence in a clinical investigation subject which does not necessarily have a causal relationship with the drug or device under study.
Age	For a given event, age will be expressed in days or months and rounded to one decimal place for months. A month is standardized to a period of 30 days.

Abbreviation	Description
	Age at Event = (Date of Event – Date of Birth + 1)/ 30 (displayed as months). Age at Baseline = (Date of Gene Therapy Infusion – Date of Birth + 1)/ 30 (displayed as months).
Baseline	Baseline, e.g., in terms of baseline laboratory values, vital signs, or physical exam results, refers to a measurement or evaluation made prior to initiation of gene therapy infusion. If there are multiple measurements prior to the initiation of gene therapy infusion, only the latest measurement in most cases will be considered as baseline for analysis purposes or defined specifically.
BiPAP	Bilevel Positive Airway Pressure, a form of non-invasive mechanical pressure support ventilation.
CHOP-INTEND	Children's Hospital of Philadelphia Infant Test of Neuromuscular Disorders, a 16-item motor function assessment validated for use in infants with spinal muscular atrophy.
CMAP	Compound Muscle Action Potential, the total electrophysiological output in a muscle or muscle group recorded by surface electrodes following supramaximal stimulation of the innervating nerve.
Day 1	The day of the gene therapy treatment
Dose	Total vector genome delivered (in vg /patient weight on Day – 1(kg)).
MedDRA	Medical Dictionary for Regulatory Activities is a medical terminology used to classify adverse event information associated with the use of biopharmaceuticals and other medical products.
CTCAE	Common Terminology Criteria for Adverse Events version 4.03. The CTCAE is descriptive terminology, involving a severity scale, which is used for AE reporting in particular for unique patient populations. It is a subset of MedDRA terminology.
Permanent Ventilation	Requirement of \geq 16-hour respiratory assistance per day (includes BiPAP) continuously for \geq 14 days in the absence of an acute reversible illness, excluding perioperative ventilation.
PNCR	Pediatric Neuromuscular Clinical Research Network

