4.6.1. Adverse Events

Other than Grade III or higher adverse events used to define unacceptable toxicity in the primary endpoint, all adverse events will be assessed for their seriousness, relatedness to study treatment, relationship to study discontinuation, and severity according to [CTCAE](#) version 4.03 criteria.

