6.2.4.4. Safety Variables

The safety endpoint is defined as the patient meeting the following criteria:

- Unanticipated toxicity event of Grade ≥ 3 (as per CTCAE)
- Adverse events of special interest (see Section 10.3.2.4)
- ‘Possibly Related’ or ‘Probably Related’ or ‘Definitely Related’ to study treatment
- Requires medical treatment or presents with symptoms

This will be collected at all scheduled visits (see [Table 1](#)) from patient’s CRF. Adverse Event collection methods for the observational natural history cohort were not consistent with rigorous Adverse Event collection methods demonstrated in the context of an interventional clinical research study; therefore, only descriptive statistics will be presented.

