10.3.2.5. Related Adverse Events by Maximum Grade

Treatment-emergent adverse events and treatment-emergent adverse events with a "possibly related", "probably related", or "definitely related" of being related to AVXS-101 will be summarized by maximum grade of each preferred term. If a patient has an adverse event with unknown grade, then the patient will be counted in the grade category of "unknown," even if the patient has another occurrence of the same event with a grade present.

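### Section 10.3.2.6 mixes seriousness into a table labelled as CTCAE grade, so its patient counts by grade can differ from those in 10.3.2.5 for the same preferred terms

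*SAP*

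**What the plan says.** **How an event is graded.** SAP section 4.6.1 says that "all adverse events will be assessed for their seriousness, relatedness to study treatment, relationship to study discontinuation, and severity according to" CTCAE version 4.03. Seriousness and severity are thus two items in one list, both recorded per event. The glossary (section 1.2) agrees: "The CTCAE is descriptive terminology, involving a severity scale, which is used for AE reporting". Section 6.2.4.4 writes the threshold of the safety endpoint as "Unanticipated toxicity event of Grade ≥ 3 (as per CTCAE").

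**First maximum-grade table.** Section 10.3.2.5 is titled as a table of related events, but its text covers all treatment-emergent adverse events (TEAEs) as well as the related ones. They "will be summarized by maximum grade of each preferred term". Its rule for missing grades begins "If a patient has an adverse event with unknown grade, then the patient will be counted in the grade category of" unknown, and applies to any adverse event.

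**Second maximum-grade table.** Section 10.3.2.6 opens with "Treatment-emergent adverse events will be summarized by maximum CTCAE grade level of each preferred term". Its next sentence is "Each preferred term will be assigned to a grade level based on severity and seriousness, adapted from CTCAE Version 4.03", and it closes by describing CTCAE as a means of grading severity. A separate sentence follows: "All serious adverse events will be categorized according to Grade definition". The unknown-grade rule here is limited to non-serious events.

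**A related summary.** Section 10.3.2.2 lists a table of Grade 3 or 4 TEAEs by system organ class and preferred term, with a parenthetical pointer to a definition further down.

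**The concern.** The two sentences that define the table in 10.3.2.6 do not agree. The first promises a CTCAE grade, which elsewhere in the SAP is a severity scale applied to each event. The second describes something else in three respects: seriousness enters the level, the scale is adapted rather than used as it stands, and the level belongs to the preferred term rather than to the event. Serious events then get a sentence of their own that refers to a definition the SAP does not contain.

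Because 10.3.2.5 already tabulates all TEAEs by maximum grade per preferred term, the report would hold two tables of the same events with nothing to say which one governs. If the counts differ, a reader cannot tell which table shows CTCAE severity. In a single-arm study of a one-time treatment in at most 20 infants, the safety description rests on small counts, and one patient in a different row is visible.

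**Working it through.** No sample size, power or event count enters, and the SAP gives no figure to reproduce. The check compares the texts and follows individual patients through both rules.

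**Inputs**

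| Item | 10.3.2.5 | 10.3.2.6 |
|---|---|---|
| Events covered | all TEAEs, and related TEAEs | all TEAEs |
| Unit of display | maximum grade per preferred term | maximum grade level per preferred term |
| Basis of grade | not defined there; CTCAE 4.03 severity if read with 1.2, 4.6.1 and 6.2.4.4 | CTCAE in the first sentence; severity with seriousness, adapted from CTCAE, in the second |
| Serious events | no separate rule | placed by an unstated grade definition |
| Unknown grade | any adverse event | non-serious adverse events only |

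**Cases**

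1. *Serious event, CTCAE Grade 2 recorded.* In 10.3.2.5 the patient is in the Grade 2 row. In 10.3.2.6 the row is Grade 2 if seriousness carries no weight, and it is undetermined if seriousness does, because no weight is given.
2. *Serious event, grade missing.* In 10.3.2.5 the patient is in the unknown row. In 10.3.2.6 the unknown rule does not apply, and the patient is placed by the unstated definition.
3. *Serious occurrence with grade missing, plus a non-serious occurrence of the same preferred term at Grade 1.* In 10.3.2.5 the patient is still unknown, because that rule overrides a known grade on another occurrence. In 10.3.2.6 nothing sends the patient to unknown. The tables differ here without any assumption about how seriousness changes a grade.
4. *Non-serious event, grade missing.* The patient is unknown in both tables.

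Cases 2 and 3 follow from the two unknown-grade rules alone. Case 1 depends on how the second sentence of 10.3.2.6 is programmed. In each, the difference lies in the number of patients per grade row within a preferred term, since both tables place each patient by maximum grade.

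**Pointer in 10.3.2.2.** The only later text in the SAP on how an adverse event grade is assigned is 10.3.2.6. If the pointer means that section, the adapted level also feeds the Grade 3 or 4 summary. The SAP does not settle this.

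**Size of one patient.** Section 3.5 allows up to 20 patients, all treated. One patient is 1/20 = 0.05, or 5 percentage points, and more if fewer are treated. The number who would move cannot be derived, because it depends on the missing definition and on events not yet observed.

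**The case against.** The strongest reply is that the reference to seriousness in 10.3.2.6 is a stray word. The section title speaks of severity, the first sentence says CTCAE grade, and the second ends by naming severity grading as the purpose of CTCAE. The sentence on serious events could mean only that they take their CTCAE grade like any other event, and a grade definition could stand in the protocol. On that reading there is one scale and some loose drafting.

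Part of this stands. The sentences can be read that way, and the absence of a definition would not be a finding by itself. But the unknown-grade rule in the same section is restricted to non-serious events, and serious events have their own sentence. Seriousness therefore operates in 10.3.2.6 even if the phrase in the second sentence is discounted, and the difference from the rule in 10.3.2.5 remains.

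Three stronger readings are tempting, and the SAP does not support them.

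- A reader might infer that serious Grade 1 or 2 events are raised to Grade 3 or higher. No sentence says so.
- A reader might infer that the primary safety endpoint or the halting criterion is compromised. Sections 3.4 and 6.2.4.4 tie the endpoint to CTCAE directly. The criterion in 2.2.3 concerns any single patient with a related Grade 3 or higher toxicity under continual monitoring, so it does not depend on a table of preferred terms.
- A reader might put a large figure on the gap by assuming how many infants have such events. Nothing in the SAP supports a count, and neither section specifies an overall rate of patients with Grade 3 or higher events that could be compared.

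**Conclusion.** The point holds as an inconsistency in the derivation of descriptive safety tables. Section 10.3.2.6 contradicts its own first sentence and section 4.6.1, and its grading of serious events cannot be reproduced from the SAP. It also differs from 10.3.2.5 in its rule for unknown grades, so patient counts by grade for the same preferred terms can disagree.

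The size is unknown beyond the step of at least 5 percentage points per patient. The conclusion assumes that grade in 10.3.2.5 means CTCAE 4.03 severity, which that section does not say but the glossary, 4.6.1 and 6.2.4.4 imply. The difference in unknown-grade rules does not need that assumption. No hypothesis test or efficacy result is touched. The Grade 3 or 4 summary in 10.3.2.2 is possibly affected, through its pointer. The correction should be made before the tables are programmed.

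**What to change.** - In 10.3.2.6, strike the reference to seriousness and to adaptation from the second sentence, and delete the sentence that places serious events by a grade definition.
- State once that every adverse event grade table uses the event-level CTCAE 4.03 severity grade recorded under 4.6.1, taking the maximum per patient and preferred term.
- Apply one unknown-grade rule in 10.3.2.5 and 10.3.2.6, the same for serious and non-serious events.
- In 10.3.2.2, replace the pointer to a later definition with a reference to CTCAE 4.03.
- Report seriousness only in the serious adverse event tables.

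Merging 10.3.2.5 and 10.3.2.6 into one table for all TEAEs and one for related TEAEs would remove the duplication, but it is optional once the definitions agree. The cost is a few lines of SAP text and matching table specifications. No data collection changes.

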10.3.2.7. Adverse Events by Maximum Relationship

Treatment-emergent adverse events also will be summarized by maximum relationship of each preferred term to study drug (AVXS-101), as assessed by the investigator. If a patient has an adverse event with unknown relationship, then the patient will be counted in the relationship category of "unknown," even if the patient has another occurrence of the same event with a relationship present. The only exception is if the patient has another occurrence of the same adverse event with a relationship assessment of "possibly related" or higher. In this case, the patient will be counted under the "related" category.

10.4. Laboratory Evaluations

10.4.1. Analysis of Laboratory Data

Safety laboratory data and genetic diagnosis laboratory data generated by local lab and by Q2, the designated central laboratory, will be used in all analyses. Immunoassay data generated by CTL will be used in all analyses.

Viral shedding data generated by PPD may not be summarized in the clinical study report; however, a separate analysis report will be completed.

10.4.2. Variables and Criteria Defining Abnormality

Hematology variables include: hematocrit, hemoglobin, red blood cell (RBC) count, white blood cell (WBC) count, lymphocytes, neutrophils, lymphocytes, monocytes, eosinophils, basophils, bands, mean corpuscular volume (MCV), mean corpuscular hemoglobin (MCH), mean cell hemoglobin concentration (MCHC), and red cell distribution width (RDW).

Chemistry variables include: albumin, alanine aminotransferase (ALT/SGPT), alkaline phosphatase, aspartate aminotransferase (AST/SGOT), blood urea nitrogen (BUN),

creatinine, gamma glutamyl transferase (GGT), glucose, serum total bilirubin, direct bilirubin, total creatine kinase (CK), CK-MB, and electrolytes.

Urinalysis variables include: specific gravity, pH, ketones, glucose, protein, blood, leukocyte esterase, nitrites, bilirubin, red blood cell (RBC) count, white blood cell (WBC) count, yeast, squamous epithelial cells, casts, crystals, bacteria.

Immunology variables include: mother's serum binding antibody titer to AAV9, serum binding antibody titer to AAV9, binding antibody titer to SMN, T-cell response to AAV9 and SMN.

The Criteria for PCS Laboratory Findings are maintained outside of this SAP.

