10.3.2.4. Adverse Events of Special Interest

The following specific treatment-emergent adverse events of special interest, which may be searched using Standardized MedDRA queries, will be summarized:

- Hepatotoxicity, identified via the following SMQs:
 - Hepatic failure, fibrosis and cirrhosis and other liver damage-related conditions (SMQ)
 - Hepatic disorders (SMQ)
- Thrombocytopenia, identified via the following SMQs/HLT:
 - Hematopoietic thrombocytopenia (SMQ)
 - Haemorrhages (SMQ)
 - All TEAEs which code into the "Platelet disorders NEC" HLT
- Cardiac events, identified via the following SMQs:
 - Ischemic heart disease (SMQ)
 - Cardiomyopathy (SMQ)
 - Cardiac arrhythmias (SMQ)
 - Embolic and thrombotic events (SMQ)
 - Myocardial infarction (SMQ)
- Ganglionitis, with potential cases identified by reviewing all TEAEs which code to the "Nervous System Disorders" SOC

For each AE of interest category, the number and percentage of patients experiencing at least one TEAE in the search for the event of interest will be presented overall. AEs of interest will be summarized by SOC and PT overall.

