10.4.3. Statistical Methods

Clinical laboratory test will be summarized at each visit during the treatment period. The baseline value will be the last measurement on or before the day of the infusion of study drug. This same baseline value will be used for all changes from baseline tables in the treatment period and post-treatment period. Natural history control data is not available for this evaluation.

Mean changes from baseline to End of Study/Early Termination will be summarized for each protocol-specified laboratory parameter with the baseline mean, visit mean, change from baseline mean, standard deviation, minimum, maximum, and median.

During the treatment period, laboratory data values will be categorized as low, normal, or high based on normal ranges of the laboratory used in this study. Shift tables from baseline to minimum value, maximum value, and final values during the treatment period will be created. The shift tables will cross tabulate the frequency of patients with baseline values below/within/above the normal range versus minimum/maximum/final values below/within/above the normal range.

The number and percentage of patients with post-baseline values during the treatment period meeting the specified criteria for Potentially Clinically Significant (PCS) laboratory values will be summarized. A post-baseline value must be more extreme than the baseline value to be considered a PCS finding. A listing will be provided that presents all of the lab values for the patients meeting PCS criteria during treatment Period.

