For hemoglobin and the liver function tests (LFTs) of ALT, AST, alkaline phosphatase, and total bilirubin, the number and percentage of patients in each treatment group with a maximum CTCAE Grade of 1, 2, 3, or 4 (as defined by the central laboratory and based on CTCAE v4.03) at any post-baseline visit (regardless of the baseline value) through the end of treatment (i.e., Final Treatment Value) will be summarized. All LFT tables will include summary rows for the number and percentage of patients with at least Grade 2 and at least Grade 3 laboratory abnormalities. The hemoglobin table will include a summary row for the number and percentage of patients with at least a Grade 2 laboratory abnormality. Listings of all ALT, AST, total, indirect and direct bilirubin, and alkaline phosphatase will be created for any patients who had at least a Grade 3 ALT, AST, alkaline phosphatase, or total bilirubin. A listing of hematology results will be provided for patients with hemoglobin abnormalities.

For patients with a Grade 3 or higher total bilirubin elevation, a listing of treatment-emergent adverse events (defined as preferred terms within the "Cholestasis and jaundice of hepatic origin" (broad search) SMQ, excluding preferred terms within the "Investigations" SOC) will be provided.

The number and percentage of patients meeting the following criteria will be summarized overall.

- ALT \geq 3x ULN with bilirubin < 2x ULN
- AST \geq 3x ULN with bilirubin < 2x ULN
- ALT \geq 5x ULN with bilirubin < 2x ULN
- AST \geq 5x ULN with bilirubin < 2x ULN
- ALT \geq 10x ULN with bilirubin < 2x ULN
- AST \geq 10x ULN with bilirubin < 2x ULN
- ALT \geq 20x ULN with bilirubin < 2x ULN
- AST \geq 20x ULN with bilirubin < 2x ULN
- ALT \geq 3x ULN with bilirubin \geq 2x ULN
- AST \geq 3x ULN with bilirubin \geq 2x ULN
- ALT \geq 5x ULN with bilirubin \geq 2x ULN
- AST \geq 5x ULN with bilirubin \geq 2x ULN
- ALT \geq 10x ULN with bilirubin \geq 2x ULN
- AST \geq 10x ULN with bilirubin \geq 2x ULN
- ALT and AST \geq 3x ULN with bilirubin < 2x ULN
- ALT and AST \geq 5x ULN with bilirubin < 2x ULN
- ALT and AST \geq 10x ULN with bilirubin < 2x ULN
- ALT and AST \geq 3x ULN with bilirubin \geq 2x ULN
- ALT and AST \geq 5x ULN with bilirubin \geq 2x ULN
- ALT and AST \geq 10x ULN with bilirubin \geq 2x ULN
- ALT and AST \geq 20x ULN with bilirubin \geq 2x ULN

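### Platelet count is not named among the hematology variables or graded by CTCAE, so the only explicit analysis of thrombocytopenia, an event of special interest, rests on coded adverse events

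*SAP*

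**What the plan says.** **Variable list (SAP 10.4.2).** The hematology list opens "Hematology variables include: hematocrit, hemoglobin, red blood cell (RBC) count, white blood cell (WBC) count, lymphocytes, neutrophils, lymphocytes, monocytes", continues with eosinophils, basophils and bands, and closes with "mean corpuscular volume (MCV), mean corpuscular hemoglobin (MCH), mean cell hemoglobin concentration (MCHC), and red cell distribution width (RDW"). Platelet count is in no part of it, and lymphocytes are named twice. The same section says that the PCS criteria for laboratory findings are held outside the SAP.

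**Special-interest events (SAP 10.3.2.4).** One of the four categories is introduced as "Thrombocytopenia, identified via the following SMQs/HLT". The search terms are two standardized queries, one for hematopoietic thrombocytopenia and one for haemorrhages, and one high-level term for platelet disorders. All three act on coded adverse events. No laboratory threshold is attached.

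**Graded table and listing (SAP 10.4.3).** The table of maximum CTCAE grade begins "For hemoglobin and the liver function tests (LFTs) of ALT, AST, alkaline phosphatase, and total bilirubin" and names no other parameter. The hematology listing is tied to the same analyte: "A listing of hematology results will be provided for patients with hemoglobin abnormalities".

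**General laboratory outputs (SAP 10.4.3).** Mean changes "will be summarized for each protocol-specified laboratory parameter". The section also plans summaries at each visit, shift tables to the minimum, maximum and final value, and counts of patients with PCS values. None of these is expressly limited to the list in 10.4.2.

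**The concern.** The direct laboratory marker of thrombocytopenia is the platelet count. The plan treats thrombocytopenia as a risk worth its own category, yet it neither names that marker as an analysis variable nor gives it a graded table.

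The emphasis is uneven. Hepatotoxicity has graded tables, listings for Grade 3 and above, and a long set of enzyme and bilirubin criteria. Hemoglobin has a graded table although anemia is not a special-interest category. Thrombocytopenia has no named laboratory analysis.

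At stake is the completeness of safety reporting on a named risk. The category also matters elsewhere: SAP 6.2.4.4 lists special-interest events and Grade 3 or higher toxicity among the criteria for the safety endpoint. A graded platelet table would be the natural cross-check on how those events were reported. No efficacy analysis and no formal test is affected.

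**Working it through.** No sample size, power or error-rate calculation bears on this point. The check is a count and a side-by-side reading.

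**1. Hematology list in 10.4.2.** The entries are hematocrit, hemoglobin, RBC, WBC, lymphocytes, neutrophils, lymphocytes, monocytes, eosinophils, basophils, bands, MCV, MCH, MCHC and RDW.
- Total entries: 15.
- Distinct entries: 15 − 1 duplicate = 14.
- Platelet entries: 0.

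**2. Parameters in the maximum-grade table in 10.4.3.** Hemoglobin, ALT, AST, alkaline phosphatase and total bilirubin: 5 parameters, none of them platelets. This list is closed, so a fuller panel in the protocol would not add platelets to it.

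**3. Laboratory criteria for hepatotoxicity in 10.4.3.**
- ALT or AST alone, bilirubin below 2 × ULN: 2 enzymes × 4 cut-offs = 8.
- ALT or AST alone, bilirubin at least 2 × ULN: 2 × 3 = 6.
- ALT and AST together, bilirubin below 2 × ULN: 3.
- ALT and AST together, bilirubin at least 2 × ULN: 4.
- Total: 8 + 6 + 3 + 4 = 21. The corresponding number of explicit criteria for platelets is 0.

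**4. Mentions of platelets in the SAP.** There is one, in 10.3.2.4, as an adverse event coding term and not as a laboratory variable.

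**5. What each planned route would show about a platelet fall.**

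| Output | Could it include platelets? | What it would show |
|---|---|---|
| Special-interest search (10.3.2.4) | Yes, if an event was reported | Coded events; also bleeding without a platelet fall, through the haemorrhage query |
| Adverse events by maximum grade (10.3.2.6) | Yes, if an event was reported | Severity of reported events only |
| By-visit and change summaries (10.4.3) | If platelets are in the protocol panel | Group summaries, with minimum and maximum |
| Shift to minimum (10.4.3) | If platelets are in the protocol panel | Low, normal or high, without grade |
| PCS counts and listing (10.4.3) | If the external document has a platelet criterion | Cannot be confirmed here |
| Maximum CTCAE grade from laboratory data (10.4.3) | No | Nothing |
| Targeted hematology listing (10.4.3) | Only for patients with a hemoglobin abnormality | Nothing for an isolated platelet fall |

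**6. From laboratory value to adverse event.** Sections 10.5 and 10.8 say that clinically significant or abnormal treatment-emergent findings for vital signs and physical examination become adverse events. Section 10.4 says nothing similar for laboratory values. The protocol may do so.

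**7. Availability of data.** Table 1 schedules hematology after dosing on Days 2, 7, 14, 21 and 30, then monthly and at the end of study. If the panel reports platelets, a graded table can be made from samples already planned.

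**The case against.** A reader might infer that thrombocytopenia is never measured from platelet data, that site reporting is the only route to it, or that the lowest value is observed but not tabulated. The document does not support any of these. The list in 10.4.2 is introduced as what the variables include and is not said to be exhaustive. The by-visit summaries, the changes for every protocol-specified parameter and the shift tables in 10.4.3 are not tied to that list. A shift to the minimum is suited to catching a transient fall. If the protocol panel contains platelets, they belong in those outputs.

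Nor is it right to call the adverse event data spontaneous reports. Table 1 makes adverse events an assessment at every visit, and the hepatic and cardiac categories are also identified by query searches.

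Two further points stand. CK-MB, which is relevant to the cardiac category, has no graded table either, and the extensive liver criteria go with a dedicated section on drug-induced liver injury. Leaving out a graded platelet table is therefore a gap and not a self-contradiction. It is also only an inference that the second lymphocytes entry was meant to be platelets; it may be a plain repetition.

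The objection does not remove the narrower point. Shift tables carry no severity grade, a platelet PCS criterion cannot be confirmed from this document, and the graded table omits platelets whatever the protocol says. A programmer working from 10.4.2 would find no platelet variable.

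**Conclusion.** The point holds in this limited form. The SAP repeats lymphocytes, does not name platelet count, and plans no CTCAE-graded summary of platelet values. Its only explicit analysis of thrombocytopenia rests on reported and coded adverse events.

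The size can be stated only as counts: 0 of 15 hematology entries, 0 of 5 graded parameters, and 0 explicit platelet criteria against 21 for liver tests. With up to 20 patients, one patient is at least 1/20 = 5 percentage points of incidence. A reader might take that as the expected error, but it is true of any event at this sample size and does not estimate how many cases would be missed.

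Two matters outside this document remain open: whether the protocol panel contains platelets, and whether the external PCS document has a platelet criterion. If both do, the general outputs cover part of the gap and only the graded table and the listing are missing. This is a low-cost correction that should be made. It changes no primary, secondary or formally tested result.

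**What to change.** - **10.4.2:** delete the duplicate lymphocytes entry and add platelet count to the hematology variables.
- **10.4.3, graded table:** add platelets, in the low direction, to the maximum-CTCAE-grade table, with rows for at least Grade 2 and at least Grade 3.
- **10.4.3, listing:** add a listing of all platelet values for any patient with at least Grade 3.
- **10.4.3, general outputs:** once platelet count is named, a short statement that the existing shift and PCS outputs apply to it would settle the remaining doubt.

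The cost is SAP wording, one table extension and one listing. No new sampling is needed, provided that the existing hematology panel reports platelets.
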